### 3.5.2.2 Imputation rules for missing or partial medication start/stop dates

- Start dates will not be imputed.
- Partial stop dates will be assumed to be the latest possible date consistent with the partial date. If day, month, and year are missing assign 'continuing' status to the stop date.

### 3.6 General Statistical Conventions

All statistical procedures will be completed using SAS version 9.4 or higher.

Unless otherwise stated, all statistical testing will be two-sided and will be performed using a significance (alpha) of 0.05. Two-sided 95% confidence intervals (CI) will be provided when relevant.

Continuous variables will be summarized using descriptive statistics, including number of subjects (n), mean, median, standard deviation (SD), minimum, and maximum. Means and medians will be rounded to one more decimal place than what is reported in the data. Standard deviations will be rounded to two more decimal places than what is reported in the data.

For categorical variables, summaries will include counts of subjects and percentages. Percentages will be rounded to one decimal place.

For summary purposes, baseline will be defined as the last available pre-dose value. All summaries will be presented by treatment group and SARS-CoV-2 serostatus at baseline, unless otherwise specified.

For any subject who receives an approved COVID19 vaccine after being dosed with INO-4800/placebo, the follow-up time will be divided to account for pre- and post- receipt of approved vaccine. For the main analyses and summaries of efficacy, data from the pre- receipt of an approved vaccine period will be used.

Subject data, including those derived, will be presented in individual subject data listings. Unless otherwise stated, unscheduled visit results will be included in date/time chronological order, within patient listings only. All listings will be sorted by treatment, subject ID, date/time, and visit. The treatment group, as well as the patient's sex and age, will be stated on each listing. Unless otherwise stated, data listings will be based on all subjects randomized (ITT population).

### 3.7 Disposition of Subjects

Subject disposition will be summarized by treatment arm and overall, as well as SARS-CoV-2 serostatus at baseline. The number and percent of subjects screened, screened failure, randomized to each trial arm, receiving the first and second dose, early terminations, and completing the study will be summarized. The

## Statistical Analysis Plan (SAP) – Phase 3 Segment

---

number of subjects randomized will be used as the denominator for the proportion calculation. The number in each analysis population will also be tabulated. Subject disposition will be listed along with inclusion or exclusion criteria that were not met for randomization, and the primary reason for early withdrawal will also be tabulated. Subject enrollment by site will also be tabulated by treatment arm and overall.

Treatment misallocations occur when a subject received a different treatment than they were randomized. In these cases:

- If a subject was randomized but not treated, then they will be reported under their randomized treatment group in the subject disposition summaries. These subjects will be included in the ITT population only.
- If a subject was treated but not randomized, then by definition they will be excluded from the efficacy analyses because randomized treatment is missing but will be included in the ITT population and in the Safety population according to the treatment actually received for all safety analyses.
- If a subject was randomized but received a different treatment, then the subject will be included according to their randomized treatment group for all efficacy analyses in the ITT/mITT population but will be excluded from the efficacy analyses in the PP population. These subjects will be included according to treatment they actually received for all safety analyses.

### 3.8 Extent of Exposure and Compliance

#### 3.8.1 Treatment Duration

Study treatment exposure will be summarized as the number of subjects receiving a total of 1 or 2 doses of product and will be presented by treatment group, as well as SARS-CoV-2 serostatus at baseline on the ITT mITT, PP, and safety populations.

#### 3.8.2 Treatment Compliance

A full course of study product administration consists of 2 doses of vaccine. A summary by treatment group, as well as SARS-CoV-2 serostatus at baseline detailing the total number of doses received will be presented along with the reason a second dose was not administered or missed. A summary of subjects receiving the second dose outside the dosing window, 25 to 31 days post first dose, will be presented.

### 3.9 Protocol Deviations/violations and exclusions from analysis sets

Protocol deviation data will be captured in the clinical trial management system. Extracts of all protocol deviations will be reviewed periodically and prior to interim and final analyses. All protocol deviations and the exclusion of participants from analysis sets will be identified prior to unblinding through clinical review input provided by the sponsor using supportive participant listings provided by the ICON GPHS statistician based upon data recorded in the clinical trial management system.

## Statistical Analysis Plan (SAP) – Phase 3 Segment

---

Further, deviations from the protocol will be classified as major or minor. Classification of major and minor protocol deviations is determined prior to participant enrollment and is outlined in detail in the protocol deviation criteria documentation managed by the clinical trial management team. A summary table presenting protocol deviations will be generated by treatment arm and SARS-CoV-2 serostatus at baseline for the ITT population. Protocol deviations will also be listed.

The number of subjects excluded from mITT, Safety, and Per-Protocol analysis sets and reasons for exclusions will be summarized by treatment group and overall, as well as SARS-CoV-2 serostatus at baseline.

Population membership details will be listed, including reason for exclusion from each population (on randomized subjects).

### 4. Baseline Characteristics and Demographics

#### 4.1 Baseline Characteristics

Age group (18-50,  $\geq$  51 years), baseline SARS-CoV-2 serostatus, and the presence of any increased risk factor (listed in SAP section [1.2.2](#)) in subjects will be summarized using frequency counts and proportions for qualitative results for the ITT and PP populations.

#### 4.2 Medical History

A summary of prior and concomitant medical conditions and surgical procedures will be presented by system organ class (SOC) and preferred term (PT) using the Medical Dictionary for Regulatory Affairs (MedDRA) version 23.0, by treatment arm and SARS-CoV-2 serostatus at baseline.

#### 4.3 Demographics

Demographic data will be summarized with descriptive statistics, including mean, standard deviation, minimum, median, and maximum values for continuous variables and frequency counts and percentages for categorical variables, by treatment arm and SARS-CoV-2 serostatus at baseline.

Age, height, weight, body mass index (BMI) and other continuous demographic variables at baseline will be summarized descriptively. Sex, primary race, ethnicity, and other categorical variables will be summarized using the ITT and PP populations.

#### 4.4 Prior and Concomitant Medications

Medications used in this study will be coded by using the World Health Organization Drug Dictionary Enhanced (WHODrug version Mar2020 B3).

## Statistical Analysis Plan (SAP) – Phase 3 Segment

Prohibited prior and concomitant medications are described in the protocol. This list includes medications for the prevention of COVID-19 and influenza vaccinations received within 2 weeks prior to the first dose of IP, or within 2 weeks of (before or after) any subsequent dose of IP.

### 4.4.1.1 Prior Medications

Prior medications are those that were stopped before the start of the trial. Data for all prior medications will be summarized descriptively by ATC class and preferred name using percentages by treatment arm and SARS-CoV-2 serostatus at baseline, for the ITT and PP populations.

### 4.4.1.2 Concomitant Medications

Concomitant medications include all medications, including vaccines, used by subjects during the course of the trial stopped on or after the start of the trial. Data for all concomitant medications will be summarized descriptively by ATC class and preferred name using percentages by treatment arm and SARS-CoV-2 serostatus at baseline, for the ITT and PP populations.

## 5. Efficacy, Immunogenicity, and Safety Analyses

### 5.1 Primary Analysis

The primary objective of this clinical trial is to evaluate the efficacy of INO-4800 in the prevention of COVID-19 disease in subjects who are SARS-CoV-2 negative at baseline.

#### 5.1.1 Primary Endpoint

The primary endpoint is the first occurrence of virologically-confirmed COVID-19 disease with onset during a surveillance period from 14 days after completion of the 2-dose regimen up to 12 months post-dose 2 (EOS) in subjects who are SARS-CoV-2 seronegative at baseline.

An independent, blinded Endpoint Adjudication Committee (EAC) will review and confirm COVID-19 cases. Details of committee's scope will be provided in the respective charter.

#### 5.1.2 Statistical Hypothesis for the Primary Efficacy Endpoint

The primary hypothesis is that INO-4800 will be efficacious relative to placebo (vaccine efficacy > 30%) among baseline SARS-CoV-2 seronegative subjects. The null hypothesis given below will be tested against the alternative hypothesis:

$$H_0: p \geq .70/(.70+k)$$

$$H_1: p < .70/(.70+k)$$

where  $p$  is the true proportion of subjects with disease who receive INO-4800 relative to the total number of subjects with disease, and  $k$  is the total amount of follow-up time in the placebo group divided by the total

## Statistical Analysis Plan (SAP) – Phase 3 Segment

amount of follow-up time in the INO-4800 group. For calculating k, an individual subject's follow-up time is either:

- the date of first disease diagnosis – date of the start of surveillance period +1 (for subjects who are cases), or
- the date of last follow-up – date of the start of surveillance period +1 (for subjects who are non-cases).

However, the trial has been terminated, and therefore, this hypothesis test will not be conducted. A confidence interval (detailed in the following section) will be used for analysis.

### 5.1.3 Analysis of Primary Efficacy

The Clopper-Pearson method will be used to compute the 95% confidence interval for the primary efficacy analysis. The outcome variable will be incidence of virologically-confirmed COVID-19 disease starting 14 days after completion of the 2-dose regimen until 12 months post-dose 2 (EOS).

This methodology is based on the assumption that the number of subjects who are cases in the INO-4800 and placebo group follows a Poisson distribution with parameter  $\lambda_v$  and  $\lambda_c$ , respectively, and conditional on total number of subjects with cases, t, the number of subjects who are cases in the INO-4800 group follows a binomial distribution with parameters (t,  $p=\lambda_v/(\lambda_v+\lambda_c)$ ). The relationship between p and efficacy is: efficacy =  $(1-(1+k)p)/(1-p)$ . The confidence interval for efficacy is  $(1-(1+k)UB_p)/(1-UB_p)$ ,  $(1-(1+k)LB_p)/(1-LB_p)$ , where UB and LB are the Clopper-Pearson upper and lower limits for the proportion, respectively.

The efficacy time frame is defined by symptoms beginning at any time starting from 14 days after Dose 2 and ending 12 months after Dose 2. Subjects identified as cases that started prior to this time point will be excluded. Subjects with multiple instances meeting the case definition will be counted only once, using the first such instance.

The PP population among those who are baseline SARS-CoV-2 seronegative will be primary for the analysis of efficacy in this trial.

The following sample SAS code will be used to construct the exact binomial method of Clopper-Pearson:

```
proc freq data = <DATASET>;
  tables <OUTCOME> /binomial(CL= CLOPPERPEARSON) ;
  exact binomial;
run;
```

### 5.1.4 Sensitivity Analysis

Efficacy analysis using the mITT population will also be conducted counting cases from 14 days post dose 1 as a supportive analysis. The ITT population will also be used for a supportive analysis counting cases starting from randomization.

### 5.1.5 Changes from Protocol-Specified Primary Efficacy Analysis

Because the trial has been terminated, neither the interim nor the final hypothesis testing will be conducted.

### 5.2 Secondary Efficacy and Immunogenicity Analyses

No secondary efficacy or immunogenicity endpoints will be analyzed.

### 5.3 Exploratory Efficacy and Immunogenicity Analyses

No exploratory efficacy or immunogenicity endpoints will be analyzed.

### 5.4 Safety Analysis

The safety endpoints include:

- The incidence of solicited and unsolicited injection site reactions.
- The incidence of solicited and unsolicited systemic adverse events (AEs) by system organ class (SOC), preferred term (PT), severity, and relationship to investigational product.
- The incidence of serious adverse events (SAEs).
- The incidence of adverse events of special interest (AESIs).
- The incidence of all-cause mortality.

Safety analyses will be conducted on the safety population and will be performed for all safety variables specified below. All safety data will be summarized and analyzed by treatment group and SARS-CoV-2 serostatus at baseline.

The safety analyses of changes from baseline to a specific time point in safety variables (e.g., laboratory parameters, vital signs, ECG) will only include subjects from the safety population who have data available from both the baseline and the time point under consideration unless otherwise specified.

#### 5.4.1 Adverse Events and Deaths

All AEs will be classified by Primary System Organ Class (SOC) and Preferred Term (PT) according to the Medical Dictionary for Regulatory Activities (MedDRA) Version 23.0 or higher.

In summaries by SOC and PT, AEs will be sorted by descending frequency within each SOC and PT according to the total number of events. In summaries by PT, AEs will be sorted by descending frequency according to the total number of events.

AEs will be classified as pre-treatment or treatment emergent (TEAE) defined as follows:

- Pre-treatment: any AE that started before the first dose date of the study treatment
- TEAE: Any AE that was newly developed at or after the first dose date of study treatment.

Details for imputing missing or partial start dates of AEs are described in SAP section [3.5.2.1](#).

AE summaries will include the following:

- All TEAEs
- Related TEAEs (AE will be defined as related if causality is either probably, possible, or definite)
- TEAEs by maximum severity, including grade  $\geq 3$
- Medically Attended AEs
- TEAEs leading to treatment discontinuation
- Serious TEAEs
- TEAEs leading to death

All AEs, including injection-site reactions, will be summarized among the Safety Population by frequency per treatment arm. These frequencies will be presented overall and separately by dose, and will depict overall, by system organ class and by preferred term, the percentage of subjects affected. In addition, an overall summary for categories above will be prepared by treatment arm.

Where a subject has the same AE, based on preferred terminology, reported multiple times in the treatment period, the subject will only be counted once at the preferred terminology level in AE frequency.

Where a subject has multiple AEs within the same system organ class in the treatment period, the subject will only be counted once at the system organ class level in AE frequency.

Adverse events by severity and separately by relationship will be summarized based on the most intense event during the treatment period and strongest relationship to study treatment, respectively.

The main summary of safety data will be based on events occurring within 30 days of any dose. For this summary, the frequency of preferred term events will be compared between study arms with risk differences and 95% confidence intervals, using the method of Miettinen and Nurminen. As this analysis will use many event categories, and produce many confidence intervals, caution should be exercised when interpreting these confidence intervals. Separate summaries will be based on events occurring within 7 days of any dose and regardless of when they occurred.

The following sample SAS code will be used to construct confidence intervals of the risk difference with the method of Miettinen and Nurminen:

```
proc freq data = <DATASET>;
  tables armcd * <OUTCOME> / riskdiff(CL=(MN));
run;
```

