## Statistical Analysis Plan (SAP) - Phase 2 Segment

---

AEs will be classified as pre-treatment or treatment emergent (TEAE) defined as follows:

- Pre-treatment: any AE that started before the first dose date of the study treatment
- TEAE: any AE that was newly developed at or after the first dose date of study treatment

Details for imputing missing or partial start dates of adverse events are described in [section 6.2](#).

AE summary tables will include the following:

- All TEAEs
- Related TEAEs (AE will be defined as related if causality is either probable, possible, or definite)
- TEAEs by maximum severity
- TEAEs leading to treatment discontinuation
- Serious TEAEs
- TEAEs leading to death

All AEs including injection-site reactions will be summarized among the Safety Population by frequency per treatment arm. These frequencies will be presented overall and separately by dose, and will depict overall, by system organ class and by preferred term, the percentage of subjects affected.

Where a subject has the same adverse event, based on preferred terminology, reported multiple times in the treatment period, the subject will only be counted once at the preferred terminology level in adverse event frequency tables.

Where a subject has multiple adverse events within the same system organ class in the treatment period, the subject will only be counted once at the system organ class level in adverse event frequency tables.

Adverse events by severity and separately by relationship will be summarized based on the most intense event during the treatment period and strongest relationship to study treatment, respectively.

The main summary of safety data will be based on events occurring within 30 days of any dose. For this summary, the frequency of preferred term events will be compared between study arms with risk differences and 95% confidence intervals, using the method of Miettinen and Nurminen. As this analysis will use many event categories, and produce many confidence intervals, caution should be exercised when interpreting these confidence intervals. Separate summaries will be based on events occurring within 7 days of any dose and regardless of when they occurred.

The following sample of SAS code will be used to construct confidence intervals of the risk difference with the method of Miettinen and Nurminen:

```
proc freq data = <DATASET>;
  tables armcd * <OUTCOME> / riskdiff(CL= MN);
```

---

```
weight <COUNT>;  
run;
```

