#### 1.2.2 Randomization and Blinding

## Statistical Analysis Plan (SAP) – Phase 3 Segment

This study is double blinded. Approximately 6714 seronegative and 402 seropositive subjects 18 years of age and older will be randomized at a 2:1 ratio to receive either active investigational product (INO-4800, 2.0 mg) or placebo (SSC-0001). See [Table 1](#). Approximately half of seronegative subjects and approximately half of seropositive subjects will be 18-50 years of age, and the other half will be  $\geq 51$  years of age as is operationally feasible. Also, approximately 711 subjects will be  $\geq 65$  years of age, if operationally feasible.

Randomization in this trial will be conducted by YPrime. Subjects will be randomized in a stratified manner according to (a) age category (18-50 years vs.  $\geq 51$  years) on Day 0, and (b) presence of or absence on Day 0 of any of the following underlying medical conditions that increase risk of severe COVID-19 disease, per CDC criteria, as listed below:

- Cancer
- Chronic kidney disease
- Chronic lung diseases, including Chronic obstructive pulmonary disease (COPD), asthma (moderate-to-severe), interstitial lung disease, cystic fibrosis, pulmonary hypertension
- Neurologic conditions including stroke or cerebrovascular disease, that do not impact cognition
- Diabetes (type 1 or type 2)
- Hypertension
- Heart conditions, such as heart failure, coronary artery disease, or cardiomyopathies
- HIV infection (CD4 count  $>200$  cells/mm $^3$  or undetectable viral load)
- Liver disease
- Obesity (BMI  $\geq 30$  kg/m $^2$ )
- Sickle cell disease or thalassemia, or
- Smoking (current or former smoker).

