## Statistical Analysis Plan (SAP) – Phase 3 Segment

- d. Intradermal injection(s) in skin preferably over deltoid region, or alternately over anterolateral quadriceps region, followed by EP at Day 0 and Day 28.
- e. Following administration of INO-4800 or placebo, EP data will be downloaded from the CELLECTRA® 2000 device and provided to Inovio.
- f. AEs to be collected from time of consent to Day 56; SAEs, MAAEs, and AESIs to be collected from time of consent to EOS.
- g. On Day 0, cellular sampling requires 64 mL of whole blood prior to 1st dose. At all other time points, collect 32 mL of whole blood. Cellular samples will be collected at selected clinical sites (estimated to include 711 subjects).
- h. On Day 0, humoral sampling requires a total of 17 mL of whole blood (two 10-mL red top serum collection tubes, each 8.5 mL of whole blood, to produce four serum aliquots of 2 mL each). At all other time points, collect 8.5 mL of whole blood in a single 10-mL red top serum collection tube to produce two serum aliquots of 2 mL each.
- i. SARS-CoV-2 antibody.
- j. The Day 0 RT-PCR results will not be required prior to dosing on that day.
- k. Day 42 visit must occur at least 10 days after Day 28 visit.
- l. Subjects will be evaluated during a "COVID-19 assessment visit" when acute COVID-19 is suspected. The assessment visit may be performed in the clinic, subject's vehicle, or at a home visit and should be completed within 3 days of symptom onset or within 3 days of a positive result of a SARS-CoV-2 test.
- m. For subjects with confirmed SARS-CoV-2 infection during the trial, a convalescent visit should be scheduled approximately 28 days after symptom onset, or in the absence of symptoms, the date of positive SARS-CoV-2 test. If acute symptoms are ongoing the site should follow up with the subject via phone call or unscheduled visit after symptom resolution or stabilization.
- n. Vital signs to be performed at COVID-19 assessment and convalescent visits include temperature, respiration rate, heart rate and oxygen saturation.
- o. Genotyping may also be performed on sample(s) collected at the COVID-19 assessment visit.
- p. Diaries to be used at selected sites only (estimated to include 711 subjects).
- q. Diary should be reviewed at the 14-day post-dose phone call or visit and collected at the next in-office visit.

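### Both SAPs define treatment-emergent AEs by onset alone, so an AE that starts before Dose 1 and worsens after it is left out of the TEAE tables

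*SAP*

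**What the plan says.** Both SAPs sort AEs into two classes. The Phase 3 SAP, section 5.4.1, defines the first as "Pre-treatment: any AE that started before the first dose date of the study treatment" and the second as "TEAE: Any AE that was newly developed at or after the first dose date of study treatment". The Phase 2 SAP, section 7.7.1, has the same pair, with the second given as "TEAE: any AE that was newly developed at or after the first dose date of study treatment".

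Collection begins before dosing. The Phase 3 SAP, Appendix A, note f, says "AEs to be collected from time of consent to Day 56", and the Phase 2 SAP, Table 2, note h, says the same. In both schedules screening runs from Day -30 to Day -1 (note a). In Phase 3 the screening and Day 0 visits may be combined.

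The listed AE summaries are then mostly confined to TEAEs, among them "Serious TEAEs" and "TEAEs leading to death". Some planned output is not confined in this way. Section 5.4.1 of the Phase 3 SAP also says "All AEs, including injection-site reactions, will be summarized among the Safety Population by frequency per treatment arm", and the Phase 2 SAP has a near-identical sentence.

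**The concern.** A TEAE table is meant to show what happened to subjects after they were dosed. An event already present at dosing that then deteriorates is part of that picture, and a rule based only on start date removes it.

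The rule also fits poorly with the SAPs' own endpoints. The incidence of SAEs is an endpoint in both segments (Phase 2 SAP, section 3.2; Phase 3 SAP, section 5.4) and is not limited to treatment-emergent events. Yet the only serious-event table either SAP names is the TEAE one.

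The date rules (Phase 2 SAP, section 6.2.1.1; Phase 3 SAP, section 3.5.2.1) lean the other way. An AE with a completely missing start date is moved to the date of first dose and so counts as treatment-emergent. Doubtful onset is therefore handled more cautiously than known deterioration after dosing.

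Safety carries more weight than usual here. By its revision history, the Phase 3 SAP was cut back to primary efficacy and safety after termination, and in Phase 2 safety is the secondary objective. Serious and fatal counts are usually small, so a few reclassified events could be visible.

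**Working it through.** No figure in the plan is at issue, so the check follows one event through the rules.

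**The event.** An AE starts between consent and Dose 1 and is ongoing at Dose 1. After dosing it becomes more severe, serious or fatal. It stays on one record with its original start date.

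**Step 1, classification.** Its start precedes the first dose date, so it meets the pre-treatment definition. It did not newly develop at or after that date, so it is not a TEAE. Neither SAP has a clause that moves it.

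**Step 2, where it is counted.**

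| Output | Phase 2 SAP | Phase 3 SAP | Event included? |
|---|---|---|---|
| All TEAEs | 7.7.1 | 5.4.1 | No |
| Related TEAEs | 7.7.1 | 5.4.1 | No |
| TEAEs by maximum severity | 7.7.1 | 5.4.1 | No |
| TEAEs leading to discontinuation | 7.7.1 | 5.4.1 | No |
| Serious TEAEs | 7.7.1 | 5.4.1 | No |
| TEAEs leading to death | 7.7.1 | 5.4.1 | No |
| Medically attended AEs | not listed | 5.4.1 | Possible, no TEAE label |
| Frequencies of all AEs by arm, SOC and PT | 7.7.1 | 5.4.1 | Possible |
| Summary of events at any time | 7.7.1 | 5.4.1 | Possible |
| All-cause mortality | not an endpoint | 5.4 | Yes, if fatal |

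Of the bulleted AE summaries, the event misses 6 of 6 in Phase 2 and 6 of 7 in Phase 3.

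**Step 3, how far the other outputs help.** They are marked possible because neither SAP reconciles them with the TEAE list, and repeat events are counted within a treatment period that is not defined. Even if the event enters them, none is specified to show that it worsened or became serious after dosing.

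**Step 4, effect on the risk difference.** Suppose a table omits a proportion m1 of subjects with such an event in the INO-4800 arm and m0 in the placebo arm. Then

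observed difference = true difference − (m1 − m0).

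If m1 = m0 the difference is unchanged. If they differ, the sign of the error follows the sign of m1 − m0, on which the documents are silent. The main risk-difference analysis uses events within 30 days of any dose and is not itself labelled TEAE-only.

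**Step 5, size.** A count would need the proportion of subjects with an AE ongoing at Dose 1, the proportion of those AEs that worsen, and the number enrolled. The documents give none of these. The 7116 in Table 1 of the Phase 3 SAP is a planned number, and section 2.2 says the trial ended before 75 cases.

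**The case against.** The strongest reply is that recording rules belong to the protocol and the CRF instructions, which are not at hand. If they require a worsening AE to be entered as a new record with a new start date, the event would count as newly developed and the gap would largely close. That is a fair caveat. Neither SAP states such a rule or refers to one, however, so their text still yields the wrong class for a record that keeps its start date.

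The gap is also narrow. It concerns only onset between consent and Dose 1, at most about 30 days, and that interval can be close to nil in Phase 3 when screening and Day 0 are combined. This stands, and it limits the size of the problem.

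A reader might infer more than the documents support:

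- **That the event vanishes from every AE summary.** It does not. The last four rows of the table above are not limited to TEAEs.
- **That the loss falls mainly on subjects with chronic disease.** Phase 3 does stratify on conditions such as "Heart conditions, such as heart failure, coronary artery disease, or cardiomyopathies" (section 1.2.2). These are existing conditions, and medical history is collected and summarized separately (section 4.2 and Appendix A). A flare after dosing would ordinarily be a new AE with a post-dose onset and would meet the TEAE definition. Nothing in the SAP says otherwise.
- **That risk differences shrink.** This needs the omitted events to be unevenly split between arms in a particular direction, which nothing establishes.
- **That a number of lost subjects can be stated.** Applying guessed rates to planned enrolment gives a figure with no basis in the documents.

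**Conclusion.** The point holds in a limited form. In both SAPs the TEAE definition omits AEs with onset before first dose that worsen, become serious or become fatal afterwards. Those events are missing from the six TEAE-labelled tables, including the serious and fatal ones. They may still appear in the summaries not limited to TEAEs, and a Phase 3 death would count in all-cause mortality.

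The conclusion assumes that the worsened AE keeps its original start date. The number affected is probably small and cannot be estimated, and no direction of bias between arms can be claimed. The change is still worth making, because the stated rule gives a wrong count in the tables where single events matter most, and correcting it is cheap.

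**What to change.** In the Phase 2 SAP (section 7.7.1) and the Phase 3 SAP (section 5.4.1), define a TEAE as any AE that starts on or after first dose, or that was present before first dose and increases in severity, becomes serious or becomes fatal on or after it. Restrict the pre-treatment class to AEs that started before first dose and did not worsen afterwards.

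The cost is one sentence in each SAP and one flag in the AE programming. The flag needs the AE data to show the worsening, either by its date or as a new record. If an AE has a single record holding only its maximum grade, post-dose worsening cannot be derived from grade alone, so this should be checked against the CRF. If the protocol already has worsening recorded as a new AE, a reference to that rule in each SAP would settle the matter.
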